# Document History

Date	Version	Author	Description
15-Sep-	1.0	PPD	New document
2017			

## 1 Introduction

This document describes the statistical analysis of the non-interventional study "TachoSil-4001" (RollOut).

#### 1.1 Title

RollOut  $-\text{Pre-Rolled TachoSil}\square$  in Laparoscopic Utilisation. A Non-Interventional Study.

#### 1.2 Protocol Number

Study Protocol Number: TachoSil-4001

### 1.4 Investigational Medicinal Product (IMP)

TachoSil Sealant matrix

## 1.5 Indications

TachoSil is indicated in adults for supportive treatment in surgery for improvement of haemostasis, to promote tissue sealing, for suture support in vascular surgery where standard techniques are insufficient, and for supportive sealing of the dura mater to prevent postoperative cerebrospinal leakage following neurological surgery (Summary of Product Characteristics; TachoSil, 13.Sep.2017)

#### 1.6 Patients

It is planned to document 120 patients in up to 12 Austrian centers.

#### 1.7 Duration of Data Collection

February 2016 (FPFV) - September 2018 (LPLV)

#### 1.8 Summary

This real-world observational study is conducted to obtain an overview on the ease of use of pre-rolled TachoSil® in laparoscopic

use, especially when performing gynaecological, urological and visceral surgery. Additionally, users' satisfaction with the product will be evaluated to confirm procedural advantages of the pre-rolled form in laparoscopic use (Study Protocol; 22. Feb. 2016).

# 1.9 Responsibilities

# Company Confidential Information

is

responsible for the analysis of this non-interventional study (NIS).

# 2 Analysis

## 2.1 Sample Size

Due to the character of this study (observational, non-interventional, no randomization or control group), only descriptive analysis will be conducted and no hypothesis will be tested. It is planned to include approximately 120 patients in this non-interventional study.

# 3 Study Objectives

- To describe ease of use and satisfaction with application of the pre-rolled TachoSil in laparoscopic procedures within approved therapeutic indication (SmPC).
- To assess whether pre-rolled TachoSil□ is a valuable tool from the surgeon's view for reducing post-surgical complications, especially bleeding and lymph leakage.
- To perform a costs analysis (length of hospital stay, avoidance of complications, cost savings etc.) based on information given by physicians and pecuniary considerations (Euro).
- To describe safety in the routine use of pre-rolled TachoSil in laparoscopic surgery.

(Study Protocol; 22. Feb. 2016)

# 4 Study Variables

Continuous variables will be analysed using minimim, maximum, arithmetic mean, median.

For discrete variables (ordinal, nominal), the frequency (absolute and relative) will be reported (arithmetic mean and median optionally).

If there are free text entries, these will be coded using dictionaries, if necessary.

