#### Statistical methods

For the analysis of data the safety population (SAF) only will be considered. The safety population consists of all patients,

- who received a patient information and who had consented to the collection, transmission and evaluation of their data (Comment: this has to be documented in the CRF and it is assumed that the consent forms are available for all patients in the corresponding study center.), and
- who underwent laparoscopic surgery in the field of gynecology, urology and visceral surgery with pre-rolled TachoSil® applied during surgery as documented in the CRF.

The SAF is used for summaries of demographic and baseline characteristics, all safety related variables and all summaries of effectiveness data. No per-protocol- set analysis will be done.

All data collected will be analyzed descriptively. In general, numerical continuous or 'quasi'-continuous data will be summarized with standard descriptive statistics including number of patients with valid data, arithmetic mean, standard deviation, minimum, median and maximum. For categorical variables tables of frequencies (absolute and relative frequencies) will be presented. The percentages are based on the number of patients in column heading unless otherwise stated. The number of patients with missing values is included in the calculation of the percentages.

Statistical analyses will be performed using validated statistical software (e.g. SAS®, SAS Institute Inc.). All statistical details including calculated variables and proposed format and content of tables will be detailed in a separate document, the statistical analysis plan (SAP). The SAP will be provided by the CRO and finalized before study database lock.

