# 11 Statistical Methods and Determination of Sample Size

In general, summary statistics (mean, median, standard deviation, minimum, and maximum) will be provided for continuous variables, and the number and percentage of each category will be provided for categorical data. Any changes in the original statistical methodology will be documented in the statistical analysis plan (SAP), a separate document provided by the CRO

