# 11.1 Statistical Analysis Plan

This study is observational and epidemiological methods will be employed for data analyses. All statistical details including calculated variables and proposed format and content of tables will be detailed in the SAP, a separate document provided by the CRO

The SAP will be finalized before study database lock. The analysis will be performed in accordance with the European Network of Centres for Pharmacoepidemiology and Pharmacovigilance (ENCePP) Guide on Methodological Standards in Pharmacoepidemiology [R5].

Statistical analyses will be performed using validated statistical software (e.g. SAS®, SAS Institute Inc.).

Descriptive analysis will be performed of all collected data except data collected only for the purpose of data cleaning. All AEs will be listed as described in the SAP in section 5.

The main outcomes of the study are:

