#### 4.1.9 Assessment

- Assessment of manageability of TachoSil (1-5)
  - o Frequencies
  - o Median / Mean

- Assessment of satisfaction with TachoSil (1-5)
  - o Frequencies
  - o Median / Mean

•

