## 4.2.2 Evaluation

- Previous TachoSil experience
  - o Frequencies
- Surgery -specific TachoSil experience
  - o Frequencies
- Assessment of satisfaction with TachoSil (1-5)
  - o Frequencies
  - o Median / Mean
- Reason for divergent satisfaction compared to Baseline evaluation
  - o Free Text, grouping if possible
- Advantage of TachoSil
  - o Reduction of surgery time (minutes)
    - Yes / No: Frequencies
    - Difference of duration of TachoSil, compared to alternative application: Maximum, median, arithmetic mean
  - o Reduction of ICU time (days)
    - Yes / No: Frequencies
    - Difference of duration of TachoSil, compared to alternative application: Maximum, median, arithmetic mean
  - o Reduction of total care time (days)
    - Yes / No: Frequencies
    - Difference of duration of TachoSil, compared to alternative application: Maximum, median, arithmetic mean
  - o Other
    - Yes / No: Frequencies
    - Free text, grouping if possible

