# 7 Analysis Details

Data analysis will be done using Statistics Software (Excel 2010, MedCalc 17.8.6).

Descriptive Statistics will be used (No testing of hypotheses):

- Number of observations
  - o Absolute
  - o Relative
- Arithmetic Mean
- Median
- Minimum
- Maximum

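### The SAP leaves out the standard deviation that the protocol lists for continuous data, and the minimum too for the claimed time savings, without flagging the change

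*SAP*

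**What the plan says.** The protocol states the rule twice. Section 11 says that "summary statistics (mean, median, standard deviation, minimum, and maximum) will be provided for continuous variables". The Statistical methods part of section 2 lists "number of patients with valid data, arithmetic mean, standard deviation, minimum, median and maximum". Both statements are worded as general rules. Section 11 adds that any change to the statistical methodology will be documented in the SAP.

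SAP section 4 sets a shorter list: "Continuous variables will be analysed using minimim, maximum, arithmetic mean, median". The descriptive statistics in SAP section 7 are the number of observations, mean, median, minimum and maximum. The item lists for continuous variables in SAP 4.1.2, 4.1.6, 4.1.7, 4.1.8 and 4.2.1 follow the same pattern. SAP 4.2.2 is shorter still for the reductions in surgery, ICU and total care time: "Difference of duration of TachoSil, compared to alternative application: Maximum, median, arithmetic mean".

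For ordinal and nominal items, SAP section 4 says: "For discrete variables (ordinal, nominal), the frequency (absolute and relative) will be reported". The primary ratings fall under this rule. SAP 4.1.9 lists "Assessment of satisfaction with TachoSil (1-5") with frequencies, median and mean, and treats manageability in the same way. SAP 4.2.2 repeats the satisfaction rating at discharge.

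On software, protocol 11.1 says: "Statistical analyses will be performed using validated statistical software", with SAS as an example. SAP section 7 says: "Data analysis will be done using Statistics Software (Excel 2010, MedCalc 17.8.6"). It does not mention validation.

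**The concern.** SAP sections 2.1 and 7 allow descriptive statistics only and no hypothesis test, so the summary tables are the study's results. A mean printed without an SD has no standard error or interval. The minimum and maximum depend on the two most extreme patients and tend to move apart as the sample grows.

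The time-saving items suffer most. They feed the cost objective, and SAP 4.2.2 would have the report show the largest claimed saving beside a mean and median, with no lower end and no measure of spread. That summary is one-sided and leans towards the favourable extreme.

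There is also a question of process. The protocol makes the SAP the place where changes of method are recorded, and this change is not recorded there.

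**Working it through.** No figure in the plan depends on this point, so there is none to reproduce. The check sets the texts side by side and then asks whether the SAP's statistics determine the spread.

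**1. Statistics listed for continuous variables**

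| Place | n | Mean | Median | Min | Max | SD |
|---|---|---|---|---|---|---|
| Protocol 2, Statistical methods | yes | yes | yes | yes | yes | yes |
| Protocol 11 | – | yes | yes | yes | yes | yes |
| SAP 4, general rule | – | yes | yes | yes | yes | no |
| SAP 7, list | yes | yes | yes | yes | yes | no |
| SAP 4.1.2, 4.1.6, 4.1.7, 4.1.8, 4.2.1 | – | yes | yes | yes | yes | no |
| SAP 4.2.2, time differences | – | yes | yes | no | yes | no |

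No SD, quartile or confidence interval appears anywhere in the SAP.

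**2. Items affected.** Age, height and weight (3); INR, Quick, partial thromboplastin time and platelet count (4); surgery duration and number of units used (2); three time differences (3). 3 + 4 + 2 + 3 = 12. The details in SAP 4.1.7 and the number of adverse events in 4.2.1 use the same list.

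**3. Do minimum, maximum, mean and median fix the SD?** These are constructed values, not trial data, with n = 120 as planned in SAP 2.1.

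- Set A: one 1, one 15, six 4s and 112 5s. Sum = 1 + 15 + 24 + 560 = 600, so the mean is 5.0; the median is 5. Sum of squared deviations = 16 + 100 + 6 = 122. SD = √(122/119) = 1.01.
- Set B: fifty-five 1s, forty-three 5s and twenty-two 15s. Sum = 55 + 215 + 330 = 600, so the mean is 5.0; the median is 5. Sum of squared deviations = 55 × 16 + 22 × 100 = 3080. SD = √(3080/119) = 5.09.

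Both sets have minimum 1 and maximum 15, so the SAP's table would print the same four numbers for each. The SDs differ about five-fold. The 95% half-width of the mean, 1.96 × SD/√120, is 0.18 for A and 0.91 for B.

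**4. Dependence of the range on n.** For normal data the simulated expected range is 5.14 SD at n = 120 (the SAP's size) and 6.03 SD at n = 465 (the protocol's size). 6.03/5.14 = 1.17, so the same population would look about 17% wider at the larger size.

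**5. Primary ratings.** Full frequencies determine the SD. With assumed counts of 60, 36, 14, 7 and 3 for scores 1 to 5, the sum is 217 and the mean is 217/120 = 1.81. The sum of squares is 517, and SD = √[(517 − 217²/120)/119] = 1.02. Nothing is lost here.

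**The case against.** The strongest reply is that this is a minor inconsistency in reporting. No hypothesis is tested, and no sample size, error rate or primary result changes. Most affected items still get a minimum and maximum, and age also gets group frequencies. SAP section 9 says that raw data will be available as Excel files, so any SD can be computed later. All of this stands. It limits the point to the planned tables, but those tables are what the report will show.

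One could also say that the general rule in SAP section 4 supplies the minimum missing from 4.2.2. That is possible, but the shorter list is given separately for each of the three time items. The two sections then disagree and need reconciling, and neither supplies an SD.

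The version caveat stands too. The SAP cites a protocol dated 22 February 2016, and the supplied one is dated 20 August 2015. A later version may have changed the list.

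A reader might infer several stronger things that the documents do not support:

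- **That the study reports no usable spread, or that its results could not be pooled.** The full frequencies of the ratings and the retained raw data speak against both.
- **That the protocol promises an SD for every continuous variable without exception.** Its wording is a general rule.
- **That Excel replaces validated software.** The SAP names MedCalc as well, SAS was only an example, and nothing supplied shows either tool to be unvalidated. The gap is that validation status is not stated.
- **That the range would look about 40% wider.** That figure compares n = 465 with n = 40 (6.03/4.32 = 1.39), and neither document plans an analysis of 40 patients.

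**Conclusion.** The point holds as a contradiction between the supplied protocol and the SAP. The SD is missing from the SAP's general rule, its list of statistics and its continuous-item lists. The minimum is also missing from the time-saving items. The SAP does not record either change, although the protocol says that it will.

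The practical loss is in the planned tables for the twelve items counted above, and it is greatest for the three time differences. The five-fold difference in SD shows that the four statistics leave the spread undetermined. It does not predict what the trial's data will look like. The primary ratings are untouched.

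The conclusion assumes that the protocol version cited by the SAP keeps the supplied version's list. If it does not, the SD may no longer contradict the protocol, but the one-sided summary in 4.2.2 would remain. The software point is secondary: a commitment in the protocol is not visibly met in the SAP. The change should be made, but it is not critical to the study.

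**What to change.** - In SAP section 4, add the SD to the rule for continuous variables. Add it to the list in section 7 and to the item lists in 4.1.2, 4.1.6, 4.1.7, 4.1.8 and 4.2.1. Section 7 already covers the number of observations.
- In SAP 4.2.2, add the minimum and the SD for the reductions in surgery, ICU and total care time.
- Quartiles would help with skewed items such as surgery duration, but neither document promises them, so they are optional.
- State the validation status of Excel 2010 and MedCalc 17.8.6 for this use, or record the departure from the protocol's commitment. An independent recomputation of the tables would be one way to support the figures, though the protocol does not require it.
- If the shorter list is intended, say so in the SAP as a change from the protocol and name the protocol version concerned.

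The cost is a few lines of SAP wording. No new data are needed, and the sample size does not change.

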## 4.1 Baseline

## 4.1.1 Informed Consent, Inclusion/Exclusion Criteria

 A valid Informed Consent, dated before start of documentation, must be present. All Inclusion Criteria must be fulfilled (and none of the Exclusion Criteria), otherwise the patient must be excluded from analysis.

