# 4 Study Objectives

- To describe ease of use and satisfaction with application of the pre-rolled TachoSil® in laparoscopic procedures within approved therapeutic indication (SmPC).
- To assess whether pre-rolled TachoSil® is a valuable tool from the surgeon's view for reducing post-surgical complications, especially bleeding and lymph leakage.
- To perform a costs analysis (length of hospital stay, avoidance of complications, cost savings etc.) based on information given by physicians and pecuniary considerations (Euro)
- To describe safety in the routine use of pre-rolled TachoSil® in laparoscopic surgery.

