#### Inclusion criteria:

- Inpatient planned for laparoscopic surgery, in the field of gynecology, urology and visceral surgery where pre-rolled TachoSil® was applied and at least 18 years of age

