#### Exclusion Criteria:

- Contraindications, such as hypersensitivity to the active pharmaceutical ingredient or to another ingredient of pre-rolled TachoSil®, according to the current SmPC.
- Patient participates in another clinical trial.

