### **10.4 Data Management**

The CRO is responsible for Data Management carried out according to a Data Management Plan. A data management plan, which will include the description of plausibility checks, will be prepared before the start of data entry.

If the written informed consent of a patient is known not to be available in spite of it being required, data for this patient is not entered into or is deleted from the database.

If a patient is erroneously included in the study more than once only the data relating to the first inclusion will be kept in the database and be available for analysis.

If a patient is included in the study in spite of being treated off-label (not according to the SmPC), data is kept in the database and analysed as described in the Statistical Analysis Plan.

The current Standard Coding Instructions for coding of medical history, concomitant illness (MedDRA), concomitant medication (WHO-Drug) and adverse events (MedDRA) must be followed.

The patients will be identified in the database only by Study ID, Site ID, patient number, year of birth, and gender.

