## 4.1.8 Documentation of Surgery

- Date of Surgery
- Type of Operation: Frequencies
- Minimal invasive technique: Frequencies
  - o Other: Coding of free text, if possible
- Duration of surgery (minutes)
  - o Minimum, maximum, median, arithmetic mean
- Conversion: yes / no: Frequencies
  - o Reason(s): Frequencies
  - o Other: Coding of free text, if possible
- Adverse Event: yes / no: Frequencies
- Main reason for prerolled TachoSil use: Frequencies
  - o Other reason: Coding of free text, if possible
- Hemostatic actions before TachoSil: Frequencies
  - o Details: Frequencies
  - o Other: Coding of free text, if possible
- Application of TachoSil: Frequencies
  - o Other: Coding of free text, if possible
- TachoSil replacing other therapy: Yes / No: Frequencies
  - o Details: Frequencies
  - o Other: Coding of free text, if possible
- Reason for Preference of TachoSil
  - o Details: Frequencies
  - o Other: Coding of free text, if possible
- Other advantages of TachoSil: Yes / No: Frequencies
  - o Details: Frequencies
  - o Other: Coding of free text, if possible
- Remodeling of TachoSil
  - o Details: Frequencies
  - o Other: Coding of free text, if possible
- Duration of TachoSil pressing: Frequencies
- Number of used TachoSil
  - o Minimum, maximum, median, arithmetic mean
- Location of TachoSil application
  - o Details: Frequencies
  - o Other: Coding of free text, if possible

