# 5 Analysis Sets

# 5.1 Safety Analysis Set

Data of all patients that are eligible, have signed the Informed Consent and have documented all mandatory forms will be analysed.

The Safety Analysis Set contains all data including demographics, surgery data, evaluation of satisfaction of TachoSil, and Adverse Events.

There is no separate Per Protocol Analysis.

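### The SAP drops treated patients with a label contraindication from its only analysis set, against the protocol's safety population, and lacks the off-label rule that protocol 10.4 says it contains

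*SAP*

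**What the plan says.** SAP 4.1.1 makes eligibility a condition of being analysed at all: "All Inclusion Criteria must be fulfilled (and none of the Exclusion Criteria), otherwise the patient must be excluded from analysis". SAP 5.1 builds this into the single analysis set: "Data of all patients that are eligible, have signed the Informed Consent and have documented all mandatory forms will be analysed". There is no other set, and the adverse event summaries in SAP 4.3 have no population of their own.

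The protocol lists two exclusion criteria (sections 2 and 8). One rests on the label: "Contraindications, such as hypersensitivity to the active pharmaceutical ingredient or to another ingredient of pre-rolled TachoSil®, according to the current SmPC". The listed inclusion criterion is "Inpatient planned for laparoscopic surgery, in the field of gynecology, urology and visceral surgery where pre-rolled TachoSil® was applied", with a minimum age of 18. It does not mention the approved indication.

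The protocol defines its safety population in section 2, under Statistical methods. A patient belongs to it by consenting to data use and by having the product applied during laparoscopic surgery in one of the three fields. Eligibility is not a condition. That population serves all safety and all effectiveness summaries.

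Protocol 10.4 foresees departures from the label. It opens with "If a patient is included in the study in spite of being treated off-label", explains this as treatment not in line with the SmPC, and continues: "data is kept in the database and analysed as described in the Statistical Analysis Plan". The SAP never mentions off-label use.

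The first objective (protocol section 4, repeated in SAP section 3) concerns ease of use and satisfaction "in laparoscopic procedures within approved therapeutic indication (SmPC". The SAP summarises the reason for use only as "Main reason for prerolled TachoSil use: Frequencies", and the ratings in SAP 4.1.9 and 4.2.2 are not split by label status.

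**The concern.** The fourth objective is to describe safety in routine use. Routine use includes the occasional patient who is treated despite a contraindication, and 10.4 shows that the protocol expected some departures from the label. An exposed, consenting patient belongs in a safety set whether or not enrolment was correct. The SAP's set keeps the name but adds a condition that the protocol's set does not have, and that condition removes exactly the patients whose exposure was contrary to the label.

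The missing off-label rule also leaves the population for the ratings undefined. Ease of use and satisfaction are the primary outcomes, and the objective they serve is limited to approved use. An analyst following the SAP cannot tell whether a patient treated outside the indication should be in those tables.

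**Working it through.** The plan gives no figure on this point to reproduce, so the check compares texts. Take patients who consented and had the product applied in laparoscopic surgery in a named field.

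| Patient | Protocol safety population (section 2) | Protocol 10.4 | SAP 4.1.1 and 5.1 |
|---|---|---|---|
| A. Has a label contraindication | In | Retained, analysed by a SAP rule | Out |
| B. Treated outside the indication; only the listed criteria count as eligibility | In | Retained, analysed by a SAP rule | In, not separated |
| C. As B, but conformity with the SmPC also counts as eligibility | In | Retained, analysed by a SAP rule | Out |

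**Row A** depends on no interpretation. The contraindication is a listed exclusion criterion, 4.1.1 removes anyone who meets one, and 5.1 repeats it. Use despite a contraindication is use not in line with the SmPC, so it falls under 10.4. The SAP conflicts with both protocol passages.

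**Rows B and C** are alternatives. Protocol section 7 describes prescribing under the marketing authorisation, and sections 7.2 and 7.4 say that a patient can be included once the physician has decided to use the product according to the local SmPC. If these statements are background, row B applies and the ratings include use that objective 1 does not cover. If they are eligibility conditions, row C applies: the ratings match objective 1, but every off-label patient is removed and 10.4 is breached more widely. The documents do not choose between the readings, and neither satisfies all passages.

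**Effect on an adverse event percentage.** Let N be all consented, treated patients, k the number excluded for ineligibility, r the proportion with an event among the N − k retained, and e the proportion among the k excluded.

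- Protocol set: [(N − k)·r + k·e] / N
- SAP set: r
- Protocol minus SAP: (k/N)·(e − r)

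The SAP figure is too low only if e exceeds r. The documents give none of k, e or r, so neither the size nor the direction of the difference can be computed.

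**Ratings.** Because the protocol's population also serves the effectiveness summaries, adopting it alone would leave off-label patients in the ratings. Objective 1 needs a separate on-label display.

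**The case against.** The strongest objection is that no event is lost. Protocol 9.3 requires adverse events to be reported whatever their cause, SAP 4.3 sends them at once to pharmacovigilance, and protocol 10.4.2 reconciles study and safety databases before lock. Protocol 11.1 then has events from both databases listed or tabulated in the final report. Exclusion from analysis is also not deletion. This largely stands: a reader might infer that serious events in contraindicated patients would be concealed, and the documents do not support that. What remains is that the SAP does not carry over the 11.1 provision, and its own frequencies and denominators would omit these patients.

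A reader might also infer that the SAP orders off-label indications to be pooled into the primary ratings. No sentence does. Pooling follows only from the SAP's silence together with one reading of eligibility, and disappears on the other.

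It is tempting to put a size on the pooling with the 18% and 9% in protocol 11.3. Those are planning values for a handling score with a different applicator and say nothing about on-label against off-label use. The SAP plans no such rate for the 1 to 5 ratings. Confidence limits on a lost event would not be outputs of this plan either, since it specifies no intervals, and removing a patient reduces the denominator as well.

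Finally, the SAP cites a protocol dated 22 February 2016, while the one supplied is dated 20 August 2015. Section 10.4 or the criteria may have changed. This is a real limit on the comparison with the protocol. It does not affect the SAP's failure to relate its ratings to the approved-use limit in its own objectives.

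**Conclusion.** The point holds for the safety set: as written, the SAP removes consented, exposed patients with a contraindication from its adverse event tables, against the protocol's safety population and against 10.4. It also holds that the SAP lacks the off-label rule that 10.4 refers to. For the ratings, the finding is an unresolved ambiguity in which each reading contradicts some part of the plan; it is not an established error in one direction.

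No numerical effect can be stated. That safety would be understated is a further inference, which needs the excluded patients to have more events than the rest, and the documents do not show this. The conclusion assumes that the later protocol cited by the SAP keeps the passages used here, and that at least one such patient is enrolled.

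**What to change.** In SAP 4.1.1 and 5.1, define the Safety Analysis Set as the protocol does in section 2, regardless of eligibility or label status, and use it for every adverse event table. Confirm the wording against the protocol version that the SAP cites.

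Add the missing off-label rule. State how label status is identified from data already collected (eligibility data, type of operation, main reason for use), and say whether the SmPC statements in protocol 7, 7.2 and 7.4 are eligibility conditions. Show ease of use and satisfaction for on-label patients alongside all patients.

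The cost is SAP wording and one derived variable, with no new data collection. There is a small downside: other reasons for use are free text, and the indication quoted in SAP 1.5 includes a condition on standard techniques being insufficient, so some patients will need a judgement. The classification rule should be written down before database lock.
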